#### 4.1.2 Combination Studies

Pralatrexate is being studied as combination treatment with gemcitabine in relapsed/refractory lymphoproliferative malignancies (PDX-009). Study PDX-009 is a Phase 1/2a, open-label, multi-center study of pralatrexate and gemcitabine administered on sequential days, or the same day depending on cohort, with vitamin B12 and folic acid supplementation to patients with relapsed or refractory lymphoproliferative malignancies. The Phase 1 portion of the study was nonrandomized, while the Phase 2 portion is randomized between same day dosing or sequential day dosing. The objectives of the study are: 1) to determine the MTD and recommended Phase 2 dose of the combination of pralatrexate and gemcitabine (Phase 1); 2) to evaluate the safety and tolerability of escalating doses of pralatrexate and gemcitabine (Phase 1); 3) to determine the PK profile of the combination of pralatrexate and gemcitabine (Phase 1 and 2a); and 4) to confirm tolerability and assess preliminary efficacy in patients with relapsed or refractory Hodgkin's lymphoma, PTCL, and B-cell lymphoma (Phase 2a).

Interim efficacy data were presented in a poster presentation at the 51st Annual American Society of Hematology Meeting on the 33 patients enrolled in this study who were evaluable for response. Four of 7 patients with Hodgkin's lymphoma, 2 of 11 patients with PTCL, and 2 of 15 patients with diffuse large B-cell lymphoma (1 of whom also had PTCL) achieved a PR. Final efficacy data will be analyzed at the completion of the study.

## 4.2 Studies in Patients with Solid Tumors

### 4.2.1 Allos Single-agent Studies

In the Phase 1 study, PDX-007, investigating pralatrexate as a single agent with vitamin supplementation in patients with relapsed NSCLC, dosing started at 150 mg/m^2 every 2 weeks and initially escalated in 40 mg/m^2 increments to 270 mg/m^2 every (q) 2 weeks. Based on the DLTs experienced in the 325 mg/m^2 cohort of Treatment Group A, the MTD for Treatment Group A was determined to be 270 mg/m^2. Cohorts in Treatment Group B were initiated at dose levels below the MTD determined for Treatment Group A to further assess the safety and tolerability of pralatrexate. The starting dose for Treatment Group B was 230 mg/m^2. Although DLTs were observed at the 190 mg/m^2 dose given every 2 of 4 weeks, these DLTs were of lower grade (2 patients both with Grade 2 mucositis) than DLTs observed in any other cohort, and therefore, this dose is the recommended Phase 2 dose.

Study PDX-011 is a Phase 2, open-label, multi-center study of pralatrexate when administered concurrently with vitamin B12 and folic acid supplementation in patients with advanced or metastatic relapsed transitional cell carcinoma (TCC) of the urinary bladder. The objectives of this study are: 1) to determine the objective response rate (CR + PR); 2) to determine the duration of response, clinical benefit rate, PFS, and OS; and 3) to evaluate the safety and tolerability of pralatrexate with concurrent vitamin B12 and folic acid supplementation in patients with advanced or metastatic relapsed TCC of the urinary bladder.

Study PDX-012 is a randomized, open-label, multi-center Phase 2b study comparing pralatrexate and erlotinib in patients with Stage IIIB/IV NSCLC who are or have been cigarette smokers. The objectives of the study are: 1) to estimate the efficacy of pralatrexate as assessed by overall survival compared to that of erlotinib; 2) to estimate the efficacy of pralatrexate as assessed by response rate compared to that of erlotinib; 3) to estimate the efficacy of pralatrexate as assessed by PFS compared to that of erlotinib; and 4) to evaluate the safety and tolerability of q 2 weeks administration of pralatrexate in patients with Stage IIIB/IV NSCLC.

Study PDX-014 is an open label, multi-center, Phase 2 study of pralatrexate in female patients with Previously-treated advanced or metastatic breast cancer who have failed prior treatment(s).

Study PDX-016 is a Phase 1, nonrandomized, open-label, single-arm, combined clinical pharmacology and clinical study to evaluate the excretion and metabolic profile of

pralatrexate and to relate these findings to concurrent PK assessments in patients with advanced cancer.

#### 4.2.2 MSKCC Studies in Patients with Solid Tumors

Study PDX-97-006 was a Phase 1, single-center, dose-escalation study to determine the MTD and schedule (weekly or biweekly) of single-agent pralatrexate. The study was conducted exclusively in patients with NSCLC, who had been previously treated with a median of 2 prior chemotherapy regimens. Thirty-five patients were enrolled and 33 were treated. Initially, pralatrexate was administered at a dose of 30 mg/m^2 weekly for 3 of 4 weeks. The protocol was amended to a q 2 weeks treatment on a 4-week cycle, with dose escalation from 15 - 170 mg/m^2. The weekly treatment with pralatrexate for 3 weeks in a 4-week cycle was dose limiting at 30 mg/m^2. Altering the treatment schedule, however, to q 2 weeks (in a 4-week cycle) allowed much higher doses to be administered. The MTD and recommended Phase 2 dose was 150 mg/m^2. One patient in Study PDX-97-006, who received the MTD of 150 mg/m^2, achieved a PR, and 6 patients achieved stable disease (SD).

Study PDX-99-053 was a Phase 2, open-label, single-center study evaluating the efficacy of single-agent pralatrexate in patients with Stage IIIB or Stage IV NSCLC. Thirty-nine patients were enrolled and treated. Patients received pralatrexate q 2 weeks on a 4-week cycle. Twenty-nine patients were treated in the 150 mg/m^2 dose group. To decrease the incidence of stomatitis, the last 10 patients enrolled were treated with 135 mg/m^2 of pralatrexate. In study PDX-99-053, the median duration of survival for all patients was 13 months (mean = 16 months), with median durations of 16 months for the 150 mg/m^2 group and 7.5 months for the 135 mg/m^2 group.

Study PDX 99-083 was a Phase 1, open-label, single-center, dose-escalation study evaluating the combination of pralatrexate with a taxane (paclitaxel or docetaxel) in adult patients with advanced solid tumors. Forty-eight patients were enrolled and treated. Forty-six of those patients had NSCLC. The initial starting dose of pralatrexate was 110 mg/m^2 combined with 175 mg/m^2 of paclitaxel administered on the same day q 2 weeks in a 4-week cycle, however, DLTs prevented determination of a tolerable dose with this combination. The MTD and recommended Phase 2 dose of the pralatrexate-docetaxel combination with vitamins was 120 mg/m^2 of pralatrexate with 35 mg/m^2 docetaxel administered on the same day once q 2 weeks. One patient in PDX-99-083 treated below the MTD (treated with pralatrexate 90 mg/m^2 + paclitaxel 175 mg/m^2, without vitamin supplementation) achieved a PR and 32 patients had SD, 10 of whom were treated without vitamins and 22 of whom received vitamins.

Study PDX 01-014 was a Phase 1, open-label, single-center, dose-escalation study to determine the MTD for pralatrexate and probenecid given in combination q 2 weeks in patients with solid tumors. Seventeen patients were enrolled. The pralatrexate dose was kept at 40 mg/m^2; the dose escalation of probenecid proceeded from 70 to 233 mg/m^2. Treatment with pralatrexate in combination with probenecid q 2 weeks on a 4-week cycle exceeded the MTD at 40 mg/m^2 pralatrexate and 233 mg/m^2 probenecid due to stomatitis. The MTD and recommended Phase 2 dose of the pralatrexate and probenecid combination

was 40 mg/m^2 of pralatrexate administered with 140 mg/m^2 probenecid q 2 weeks. No patient achieved a CR or PR, but 5 patients experienced SD. The combination of pralatrexate with probenecid did not demonstrate enhanced therapeutic activity and the dose levels that were tolerated were limited.

Study PDX 01-076 was a Phase 2, open-label, single-center study in patients with unresectable malignant pleural mesothelioma. Seventeen patients were enrolled and 16 patients were treated. The dose of pralatrexate was 135 mg/m^2 intravenous (IV) q 2 weeks on a 4-week cycle. No patient in the study achieved a CR or a PR; however, 10 patients had SD (duration range: 2+ to 47 months). The median time to progressive disease (PD) for all 16 patients treated in the study was 3 months. The median duration of survival for all 16 patients was 5.5 months.

### 4.3 Safety Overview of Oncology Patients Receiving Pralatrexate

#### 4.3.1 Precautions

*Bone marrow suppression:* Pralatrexate may suppress bone marrow function, manifested by neutropenia, thrombocytopenia, and anemia. Dose modifications are described in Section 7.4 (Table 7.1) based on absolute neutrophil count (ANC) and platelet counts prior to each dose.

*Mucositis:* Treatment with pralatrexate may cause mucositis. If  $\geq$  Grade 2 mucositis is observed, the dose should be modified according to Section 7.4, Table 7.2.

*Dermatologic reactions:* Pralatrexate has been associated with severe dermatologic reactions, which may result in death. These dermatologic reactions have been reported in clinical studies (14/663 patients [2.1%]) and post marketing experience, and have included skin exfoliation, ulceration, and toxic epidermal necrolysis (TEN). These reactions may be progressive and increase in severity with further treatment, and may involve skin and subcutaneous sites of known lymphoma. Patients with skin reactions must be monitored closely, and if skin reactions are severe, study treatment may be modified or discontinued (see Section 7.4, Table 7.3).

*Tumor lysis syndrome:* Tumor lysis syndrome has been reported in patients with lymphoma receiving pralatrexate. Patients receiving pralatrexate should be monitored closely and treated for complications.

*Folic acid and vitamin B12 supplementation:* Patients must be instructed to take folic acid and vitamin B12 to potentially reduce treatment-related hematological toxicity and mucositis (see Section 7.1).

*Pregnancy and breastfeeding:* Pralatrexate may cause fetal harm when administered to a pregnant woman. Pralatrexate was embryotoxic and fetotoxic in rats and rabbits. It is not known whether pralatrexate is excreted in human milk. Many drugs are excreted in human milk and there is the potential for serious adverse reactions in nursing infants from this drug.

Study treatment must not be administered during pregnancy or when breastfeeding (see [Section 14.7](#)).

*Renal impairment:* Pralatrexate has not been formally tested in patients with moderate and severe renal impairment. Patients must have adequate renal function to be eligible for inclusion in this study, as defined in [Section 8.3](#).

*Hepatic impairment:* Pralatrexate has not been formally tested in patients with hepatic impairment. Patients must have adequate hepatic function to be eligible for inclusion in this study, as defined in [Section 8.3](#). Liver function test abnormalities have been observed after pralatrexate administration, but are usually not cause for modification of pralatrexate treatment. However, persistent liver function test abnormalities may be indicators of liver toxicity and may require dose modification (see [Table 7.3](#)).

Patients receiving pralatrexate should be monitored closely because AEs may occur at any time during therapy. For detailed information about the safety profile of pralatrexate, refer to the current pralatrexate IB.

## **4.4 Clinical Pharmacology**

### **4.4.1 Pharmacokinetics**

Pralatrexate *R* and *S* diastereomers follow apparent first-order PK with the area under the curve to infinity ( $AUC_{\infty}$ ) increasing in a near linear manner with dose. Total, renal, and non-renal clearances as well as volume of distribution were constant within (nominal) doses ranging from 30 mg/m^2 to 325 mg/m^2. Comparing the 2 diastereomers, plasma exposures of the *R* diastereomer exceed those of the *S* diastereomer by approximately 2-fold; the reason for this is unclear at this point. For a more detailed description of pralatrexate PK and population PK (POPPK), see the pralatrexate IB.

## 5 RATIONALE FOR THE CURRENT STUDY

Patients with PTCL are in need of additional treatment options. Pralatrexate exhibited encouraging activity in nonclinical in vitro and in vivo models of lymphoma. This activity was evaluated clinically in a Phase 1/2 study (PDX-02-078) in patients with lymphoma in which a response rate of 54% was observed in patients with T-cell lymphoma. Efficacy analyses from the Phase 2 study PDX-008, which was conducted in patients with relapsed or refractory PTCL, indicates that pralatrexate exhibited clinically significant activity in the patients under study, demonstrating an overall response rate of 29% and median duration of response of 10.1 months.

CHOP and CHOP-based treatments are the most commonly used therapeutic regimens for patients with newly diagnosed PTCL. However, as a majority of these patients progress or relapse following CHOP, the PFS outcome for patients responding to CHOP remains dismal. In the PDX-008 study, 15 evaluable patients received pralatrexate as their second-line treatment after CHOP, 7 of whom (47%) responded to pralatrexate by central review. Based on the responses observed in the PDX-008 study, the current protocol will determine for those patients who respond to CHOP therapy whether pralatrexate administered directly after completion of a CHOP regimen can improve PFS and OS relative to observation directly after completion of a CHOP regimen.

As described in [Section 4.1.1](#), pralatrexate administered at 30 mg/m^2 has been tolerated and demonstrated to have a therapeutic effect in patients with lymphoma in studies PDX-02-078 and PDX-008. The proposed dosing regimen for this study includes weekly dosing for 3 weeks followed by 1 week of rest. This differs slightly from PDX-008, which utilized a dosing regimen of weekly administration for 6 weeks followed by 1 week of rest. An analysis of the PDX-008 results revealed that of the 57 treated patients who received the first 3 doses without a dose modification, 24 patients (42%) required a dose modification, including possibly treatment discontinuation, prior to the rest week, ie, at either doses 4, 5, or 6. Thus, allowing a break after 3 doses may increase the long-term tolerability to full-dose pralatrexate. Therefore, the initial dose and frequency of pralatrexate in PDX-017 will be 30 mg/m^2 administered IV weekly for 3 weeks, with 1 week rest (4-week cycle), with subsequent dose reduction(s) based on toxicity. All patients will receive vitamin supplementation consisting of vitamin B12 and folic acid.

## **6 STUDY OBJECTIVES**

The primary objective of this study is:

- Determine the efficacy of pralatrexate compared to observation when administered to patients with previously undiagnosed PTCL who have achieved an objective response after completing at least 6 cycles of CHOP-based treatment.

The secondary objective of this study is:

- Determine the safety of pralatrexate when administered following a course of CHOP-based treatment to patients with previously undiagnosed PTCL.

## 7 INVESTIGATIONAL PLAN

This is an international, multi-center, randomized, Phase 3, open-label study of sequential pralatrexate versus observation in patients who have achieved an objective response following initial treatment with CHOP-based chemotherapy in patients with previously undiagnosed PTCL. Patients will be randomized 2:1 to either pralatrexate or observation. Patients will be stratified by:

- Response per investigator at completion of CHOP-based therapy (CR vs PR)

### 7.1 Vitamin Administration

Vitamin supplementation for patients in both arms of the study will consist of vitamin B12 1 mg intramuscular (IM) every 8-10 weeks and folic acid 1-1.25 mg orally (po) once a day (qd). Vitamin supplementation will begin at least 7 days prior to the projected initiation of pralatrexate/observation and continue throughout the study until the Initial Follow-up Visit ([Section 10.7](#)).

### 7.2 Pralatrexate Administration

One cycle of pralatrexate therapy is 4 weeks in duration and consists of 3 weekly doses of pralatrexate IV push over 30 seconds and up to 5 minutes, with 1 week of rest. The initial dose of pralatrexate will be 30 mg/m^2/week. For patients with a body surface area (BSA) > 2 m^2, the administered dose will be calculated using a capped BSA value of 2 m^2. Pralatrexate dose reduction to 20 mg/m^2 with further reduction to 15 and 10 mg/m^2 will be allowed for defined toxicities (see [Section 7.4](#)). Pralatrexate will continue to be administered until a criterion for study treatment discontinuation is met ([Section 7.3](#)) or up to a maximum of 2 years.

### 7.3 Study Duration

Patients will receive study treatment (pralatrexate or observation) until one of the criteria listed below for study treatment discontinuation applies:

- Development of PD
- Initiation of radiation therapy (RT) or systemic chemo/biological therapy for treatment of PTCL
- Receipt of systemic steroids for > 10 days, with the exception of those as stated in exclusion criterion #5 (see [Section 8.4](#))
- Development of an AE that interferes with the patient's participation
- Lost to follow-up
- Patient decision
- Investigator decision
- Sponsor decision

In addition, for those patients randomized to the Pralatrexate Arm, additional pralatrexate treatment discontinuation criteria are:

- 3 or more consecutive doses of pralatrexate omitted or more than 28 days between doses of pralatrexate
- Treatment with pralatrexate for 2 years

All patients who receive at least 1 dose of pralatrexate will be followed for safety through 35 ( $\pm$  5) days after their last dose of pralatrexate or until all treatment-related AEs have resolved or returned to baseline/Grade 1, whichever is longer, or until it is determined that the outcome will not change with further follow-up.

Patients who are randomized to the Observation Arm who do not discontinue the study within 3 days of randomization will be followed for safety until 35 ( $\pm$  5) days after study treatment discontinuation criteria are met.

All patients who are randomized will be followed until objectively documented PD for up to 7 years from randomization. The details of response follow-up are provided in [Section 10.8](#). PD will be confirmed by central review until the first PFS analysis, see [Section 15.6.1](#), and per investigator assessment thereafter. Subsequent therapies for PTCL will be collected for up to 7 years from randomization; the best response to the first subsequent therapy will be collected. Survival follow-up will continue for up to 7 years from randomization.

As discussed in [Section 15.6.1](#), an analysis will be performed when both 280 PFS events and 128 OS events have occurred. If the PFS analysis is not significant at the 0.05 level, the study will be stopped.

## 7.4 Treatment Modifications of Pralatrexate

Pralatrexate dose modifications will be allowed according to the criteria outlined below in [Table 7.1](#), [Table 7.2](#), and [Table 7.3](#). Dose reduction to 20 mg/m^2 with further reductions to 15 mg/m^2 and 10 mg/m^2 will be allowed for the toxicities defined in the tables below. If an AE occurs that prevents the administration of pralatrexate on the scheduled dosing day ( $\pm$  1 day), the dose will be omitted that week and the patient will be reassessed the following week to proceed to the next dose of the cycle.

### 7.4.1 Hematological Adverse Events

Treatment modification for **hematological** AEs occurring on the planned dosing day will be made as outlined in Table 7.1.

**Table 7.1. Pralatrexate Treatment Modifications for Hematological AEs**

Hematological Parameter on Planned Dosing Day	Action
ANC $\geq$ 1000/ $\mu$ L ( $\leq$ Grade 2) or platelets $\geq$ 50,000/ $\mu$ L ( $\leq$ Grade 2)	
 
No change in pralatrexate dose.
 

ANC $\geq$ 500/ $\mu$ L and $<$ 1,000/ $\mu$ L (Grade 3) without fever	
 
Administer cytokine prophylaxis and/or treatment per ASCO guidelines.
 
Do not administer pralatrexate until recovery to <math>\leq</math> Grade 2 (<math>\geq</math> 1000/<math>\mu</math>L). Upon recovery to <math>\leq</math> Grade 2, administer pralatrexate without a change in dose.
 

ANC $\geq$ 500/ $\mu$ L and $<$ 1,000/ $\mu$ L (Grade 3) associated with single oral temperature $\geq$ 38.1°C requiring parenteral antibiotics or ANC $<$ 500/ $\mu$ L (Grade 4)	
 
Administer cytokine prophylaxis and/or treatment per ASCO guidelines.
 
Do not administer pralatrexate until recovery to <math>\leq</math> Grade 2 (<math>\geq</math> 1000/<math>\mu</math>L). Upon recovery to <math>\leq</math> Grade 2, administer pralatrexate without a change in dose.
 
If reoccurrence within 28 days, reduce the pralatrexate dose to the next lower dose level.
 
Discontinue pralatrexate if event reoccurs at 10 mg/m^2 despite cytokine support.
 

Platelets $<$ 50,000/ $\mu$ L ( $\geq$ Grade 3)	
 
Do not administer pralatrexate until recovery to <math>\leq</math> Grade 2 (<math>\geq</math> 50,000/<math>\mu</math>L). Upon recovery to <math>\leq</math> Grade 2, administer pralatrexate without a change in dose.
 
If a platelet count of Grade 4 (<math><</math> 25,000/<math>\mu</math>L) reoccurs within 28 days, reduce the pralatrexate dose to the next lower dose level.
 
Discontinue pralatrexate if a platelet count of Grade 4 (<math><</math> 25,000/<math>\mu</math>L) occurs twice within 28 days at 10 mg/m^2.
 

ANC – absolute neutrophil count

°C – degrees Celsius

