### 7.4.2 Non-hematological Adverse Events

For all instances of **mucositis** occurring on the planned dosing day, treatment modifications will be made as outlined in Table 7.2. For **treatment-related cardiovascular, dermatological, hepatic, neurologic, renal, or respiratory** AEs, treatment modifications will be made as outlined in Table 7.3. For all other non-hematological treatment-related AEs, treatment modifications should be made at the investigator’s discretion.

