**Table 7.2. Pralatrexate Treatment Modifications for Mucositis**

Mucositis Grade on Planned Dosing Day	Action
0 or 1	
 
No change in pralatrexate dose.
 

2	
 
Omit this week's dose of pralatrexate. Administer with no change in pralatrexate dose if resolution to Grade 0-1.
 
If reoccurrence, omit this week's dose, upon resolution to Grade 0-1, reduce the dose to next lower dose level.
 

3	
Do not administer pralatrexate until recovery to Grade 0-1.
 
 
Upon recovery to Grade 0-1, reduce to next lower dose level
 
Discontinue pralatrexate if <math>\geq</math> Grade 3 mucositis persists for <math>\geq 2</math> consecutive weeks or reoccurs within 28 days if on <math>10 \text{ mg/m}^2</math>
 

4	
 
Discontinue pralatrexate.
 

**Table 7.3. Pralatrexate Treatment Modifications for Treatment-related Cardiovascular, Dermatological, Hepatic, Neurologic, Renal, or Respiratory AEs**

Event Grade	Action
0-2	
 
No change in pralatrexate dose.
 

3	
Do not administer pralatrexate until recovery to <math>\leq</math> Grade 2.
 
 
Upon recovery to <math>\leq</math> Grade 2 administer pralatrexate without a change in dose.
 
If the patient experiences the same Grade 3 treatment-related AE do not administer until recovery to <math>\leq</math> Grade 2 and administer with a reduction to the next lower dose level.
 
Discontinue pralatrexate if the same Grade 3 treatment-related AE recurs within 28 days at <math>10 \text{ mg/m}^2</math>.
 

4	
 
Discontinue pralatrexate.
 

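### Table 7.1 gives no explicit hold for Grade 3 neutropenia with fever not requiring parenteral antibiotics when platelets are adequate; secondarily, the row 1 'or' should be 'and'

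*Protocol*

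**What the plan says.** Section 7.4.1 of the protocol directs that hematological events on the planned dosing day be handled by Table 7.1. The bone marrow item in Section 4.3.1 points to the same table. Numbering the rows from the top:

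- **Row 1:** "ANC $\geq$ 1000/ $\mu$ L ( $\leq$ Grade 2) or platelets $\geq$ 50,000/ $\mu$ L ( $\leq$ Grade 2"). Action: dose unchanged.
- **Row 2:** "ANC $\geq$ 500/ $\mu$ L and $<$ 1,000/ $\mu$ L (Grade 3) without fever". Action: cytokine support; hold until ANC is at least 1000/µL; resume at the same dose.
- **Row 3:** Grade 3 ANC "associated with single oral temperature $\geq$ 38.1°C requiring parenteral antibiotics", or ANC below 500/µL. Action: cytokine support and the same hold, plus "If reoccurrence within 28 days, reduce the pralatrexate dose to the next lower dose level", and discontinuation on recurrence at 10 mg/m² despite cytokine support.
- **Row 4:** platelets below 50,000/µL. Action: hold until recovery, with reduction or discontinuation steps for repeated counts below 25,000/µL.

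Rows 2 to 4 each carry the instruction "Do not administer pralatrexate until recovery to" Grade 2 or better. The table does not rank its rows.

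Elsewhere, Section 7.4 says that if an AE prevents dosing on the scheduled day, "the dose will be omitted that week and the patient will be reassessed the following week". Sections 10.4.2 (item 5) and 10.4.3 (item 8) allow a dose only if no AE warrants modification or discontinuation, and both refer to Section 7.4 for the criteria. Only cycle 1 dose 1 has its own laboratory gate (Section 10.4.1, item 5: ANC at least 1000/µL and platelets at least 100,000/µL).

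**The concern.** Rows 2 and 3 appear meant to divide Grade 3 ANC between them, but their conditions are not complements. Row 2 requires no fever. Row 3 requires fever and a need for parenteral antibiotics. A patient with fever managed without parenteral antibiotics meets neither. With adequate platelets, the only row that patient meets is row 1, through its platelet limb.

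The stake is patient safety under a cytotoxic drug. A febrile patient with Grade 3 neutropenia gets less explicit protection than an afebrile patient with the same ANC. The febrile patient also misses the cytokine instruction that rows 2 and 3 both carry, and Section 13.2 ties growth-factor use to this table.

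The 'or' in row 1 is a second, smaller problem. Read literally, one adequate count is enough to meet row 1 even when the other count falls in a hold row.

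**Working it through.** The plan states no figure to reproduce. The check is whether the four row conditions cover every state once.

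**Inputs (Table 7.1).** ANC states:

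- a: at least 1000/µL
- b: 500-999/µL without fever
- c: 500-999/µL with temperature of at least 38.1°C requiring parenteral antibiotics, or below 500/µL
- d: 500-999/µL with fever not requiring parenteral antibiotics

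Platelet states: 1, at least 50,000/µL; 2, below 50,000/µL. States: 4 × 2 = 8.

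| State | Rows met as written | Row 1 with 'and' only | 'And' plus widened row 2 |
|---|---|---|---|
| a1 | 1 | 1 | 1 |
| a2 | 1, 4 | 4 | 4 |
| b1 | 1, 2 | 2 | 2 |
| b2 | 2, 4 | 2, 4 | 2, 4 |
| c1 | 1, 3 | 3 | 3 |
| c2 | 3, 4 | 3, 4 | 3, 4 |
| d1 | 1 | none | 2 |
| d2 | 4 | 4 | 2, 4 |

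**As written.** Row 1 applies to a1, a2, b1, c1 and d1, which is 5 of 8. One is correct (a1). Three also meet a hold row (a2, b1, c1). One is a low-count state with no hold row (d1). State d2 is held through row 4, so the gap needs adequate platelets.

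**With 'and' alone.** Overlaps between row 1 and a hold row fall from 3 to 0, but d1 then meets no row. The conjunction does not close the gap.

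**With 'and' and row 2 widened.** Overlaps with row 1 are 0 and uncovered states are 0. States b2, c2 and d2 meet two hold rows, so a precedence sentence is useful.

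**Sensitivity to the partition.** A finer grid (three ANC bands × three platelet bands × three fever states = 27 cells) gives 11 overlaps as written. It still gives exactly one cell at Grade 3 or worse that meets row 1 only, and it is the same one. With 'and' alone, overlaps are 0 and that cell meets no row.

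**Does another section supply the hold for d1?**

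- Section 10.4.1 does, but only at cycle 1 dose 1.
- Sections 10.4.2 and 10.4.3 take their criteria from Section 7.4, which has none for this state.
- Section 7.4.2 says "For all other non-hematological treatment-related AEs, treatment modifications should be made at the" investigator's discretion. That could reach the fever but sets no ANC hold.
- Section 7.4's omission rule presupposes that the AE prevents dosing and does not say that this one does.

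**If row 1 is about dose level only.** Table 7.2 pairs omission of a Grade 2 mucositis dose with "Administer with no change in pralatrexate dose if resolution to Grade 0-1", so an unchanged dose need not mean that a dose is given that day. On that reading row 1 conflicts only with the reduce or discontinue steps in row 3 (c1) and in row 4 (a2, and there only for repeated platelets below 25,000/µL). Row 2 has no such step. State d1 still has no hold instruction.

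**The case against.** The strongest reply is that sensible reading removes most of this.

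- **Parameter by parameter.** The hold rows each address one lineage, and Section 4.3.1 bases modification on both counts before each dose. Read that way, row 1 says only that an adequate parameter prompts no change, and the overlaps disappear. This largely stands, and it is why the 'or' is secondary.
- **Fever as the complement of row 3.** The table does not define fever separately, so row 2's condition could mean any Grade 3 ANC that does not meet row 3. Every such ANC would then be held. The reading is reasonable and probably intended, but the text does not state it, and row 3's antibiotic qualifier implies fevers that do not need them.
- **Other safeguards.** Section 7.4's omission rule, the discontinuation criteria in Sections 7.3 and 11.1, and clinical judgement would often stop the dose. These are discretionary, but they narrow the practical consequence.

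A reader might infer that the protocol directs dosing of febrile neutropenic patients. The documents do not support that: row 1 speaks of an unchanged dose, and on the parameter or dose-level reading the table is silent on d1. A reader might also infer that one adequate count permits dosing despite a Grade 4 count in the other lineage. The explicit hold rows and the dosing steps in Sections 10.4.2 and 10.4.3 point the other way.

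**Conclusion.** The gap is real on the literal text and narrow: Grade 3 ANC, fever not requiring parenteral antibiotics, platelets at least 50,000/µL, from cycle 1 dose 2 onward. It is 1 of 8 table states, and no other section supplies an explicit hold. The 'or' produces 3 overlapping states of 8 when read literally, with modest practical risk because the intent to hold is fairly clear.

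These are counts of table states, not of patients or doses, and the documents give no basis for a frequency. The conclusion on the gap assumes that 'without fever' is read as written; if it is read as the complement of row 3, the gap closes. The point merits correction because this is the operative safety rule for a cytotoxic drug. It has no bearing on the statistical design.

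**What to change.** Make three edits together, by amendment or clarification letter:

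1. **Row 2 condition:** *ANC ≥ 500/µL and < 1,000/µL (Grade 3) not meeting the criteria of the next row.* This holds every Grade 3 ANC and extends the cytokine instruction to the missing state. The added patients would follow row 2, which has no dose-reduction step.
2. **Row 1 condition:** *ANC ≥ 1000/µL and platelets ≥ 50,000/µL.* **Row 1 action:** *Administer; no change in dose unless a reduction or discontinuation step below applies.* The action wording is needed because, once counts recover, only row 1 applies, and a precedence rule alone would not preserve a reduction that is due.
3. **Section 7.4.1:** add *If more than one row applies, the most restrictive governs.*

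Edit 2 without edit 1 would leave the febrile Grade 3 state in no row. The cost is wording changes in two table rows and one added sentence, with no change to sample size, alpha or analyses.
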